9 SAFETY REPORTING

9.1 Temporary halt for reasons of subject safety

In accordance to section 10, subsection 4, of the WMO, the sponsor will suspend the study if there is sufficient ground that continuation of the study will jeopardize subject health or safety. The sponsor will notify the accredited METC without undue delay of a temporary halt including the reason for such an action. The study will be suspended pending a further positive decision by the accredited METC. The investigator will take care that all subjects are kept informed.

9.2 AE's, SAE's and SUSAR's

9.2.1 Adverse events (AE's)

Adverse events are defined as any undesirable experience occurring to a subject during the study, whether or not considered related to the investigational product, trial procedure and/or the experimental intervention. All adverse events reported spontaneously by the subject or observed by the investigator or his staff will be recorded.

9.2.2 Serious adverse events (SAE's)

A serious adverse event is any untoward medical occurrence or effect that

- results in death;
- is life threatening (at the time of the event);
- requires hospitalisation or prolongation of existing inpatients' hospitalisation;
- results in persistent or significant disability or incapacity;
- is a congenital anomaly or birth defect;
- or any other important medical event that did not result in any of the outcomes listed above due to medical or surgical intervention but could have been based upon appropriate judgement by the investigator.

An elective hospital admission will not be considered as a serious adverse event.

The sponsor will report the SAEs through the web portal *ToetsingOnline* to the accredited METC that approved the protocol, within 7 days of first knowledge for SAEs that result in death or are life threatening followed by a period of maximum of 8 days to complete the initial preliminary report. All other SAEs will be reported within a period of maximum 15 days after the sponsor has first knowledge of the serious adverse events. The product summaries for rocuronium and sugammadex will be used to evaluate whether the adverse event or reaction is expected or unexpected. The following adverse events are considered to be inevitable in surgery and will not be recorded: blood loss <500 ml, surgical site infection and wound dehiscence. However, if any of these complications is considered an serious adverse event, they will be recorded.

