Rationale: Intra-abdominal pressure (IAP) needed to create sufficient workspace during laparoscopic surgery affects the surrounding organs with ischemia-reperfusion injury and a systemic immune response. This effect is related to postoperative recovery, pain scores, opioid consumption, bowel function recovery, morbidity and possibly mortality. In clinical practice standard pressures of 12-16mmHg are applied instead of the lowest possible IAP, but accumulating evidence shows lower pressure pneumoperitoneum (PNP) (6-8mmHg) to be non-compromising for sufficient workspace, when combined with deep neuromuscular blockade (NMB) in a vast majority of patients. Therefore, low impact laparoscopy, meaning low pressure PNP facilitated by deep NMB, could be a valuable addition to Enhanced Recovery After Surgery (ERAS) Protocols.

Increased IAP can cause peritoneal mesothelial injury either directly or by compression of small vessels including capillaries, leading to a variable degree of ischemia reperfusion injury. The compromised perfusion of the parietal peritoneum can be visualized and quantified by a fluorescent marker such as Indocyanine green (ICG), as shown in a previous pilot study. Hypoxic injury of intra-abdominal organs and/or tissues may cause the release of Danger Associated Molecular Patterns (DAMPs). It is known that after trauma and sepsis, the release of DAMPs is associated with immunoparalysis and a higher susceptibility to infectious complications. The use of low pressure PNP may reduce hypoxic injury and the release of DAMPs and thereby contributing to a better preservation of innate immune function which may help to reduce the risk of infectious complications.

Objective:

Primary objectives:

- To establish the relationship between the use of deep neuromuscular blockade (NMB) with low pressure pneumoperitoneum (PNP) and the quality of recovery after RARP.
- To establish the relationship between the use of deep neuromuscular blockade (NMB) with low pressure pneumoperitoneum (PNP) and innate immune function after RARP.

Secondary objectives:

- To study whether low pressure PNP and/or deep NMB affects the perfusion of the parietal peritoneal layer during RARP.

Study design: A mono-center, randomized controlled clinical trial.

Study population: Adult patients undergoing elective RARP without extended lymph node dissection.

Intervention: The participants will be randomly assigned in a 1:1 fashion to:

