- ex vivo innate immune function,
- clinical outcomes i.e. pain scores, quality of recovery and (infectious) complications.

The study is designed to reveal the precise mechanism underlying the clinical benefits of the use of low-pressure PNP facilitated by deep NMB.

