8.2 Other study parameters

General

- Baseline parameters as age, gender, length, weight, body mass index, comorbidity, indication for and type of surgery.
- Intraoperative parameters routinely measured (at administration of ICG): blood pressure, temperature and level of NMB (train of four response).

Questionnaires

- Quality of recovery score (QoR-40) at 1 day before surgery and day 10-12 after surgery.
- SF-36 general health questionnaire (Dutch version) 1 day before surgery, day 10-12 and 3 months after surgery.
- McGill pain Questionnaire 3 months after surgery

Pain scores

- Pain at rest and movement (NRS 0-10) at 1, 8, 24, 72 hours after surgery
- Is pain acceptable (yes/no) at 1, 8, 24, 72 hours after surgery
- Referred shoulder pain (yes/no) at 1, 8, 24, 72 hours after surgery

PONV

- PONV (yes/no) at 1, 8, 24 and 72 hours after surgery

Medication use

- Cumulative opiate use
- Cumulative use of other analgesics and anti-emetics

Clinical parameters

- Time to reach discharge criteria*
- Length of hospital stay
- Surgical conditions: Leiden Surgical Rating Scale to quantify the quality of the surgical field during the pneumoperitoneum phase (after introduction of the Hasson trocar, after introduction of the third trocar and then every 15 minutes)
- Postoperative complications scored by Clavien Dindo classification (table 2 (1))

Immune function

- Peritoneal mesothelial hypoxia as reflected by peritoneal HIF1-alfa mRNA expression
- Histological peritoneal mesothelial cell injury.
- Plasma levels of DAMPs, cytokines and ex vivo immune function at baseline, 24 hours after surgery and 10-12 days after surgery.

*discharge criteria are: adequate pain control with oral medication, passage of flatus or defecation, intake of solid food tolerated, patient is mobilized and independent and patient accepts discharge. Discharge criteria will be evaluated daily. If the donor for social reasons wants to stay longer (e.g. long distance from partner of child who are still hospitalized) the 'virtual' discharge date is listed. A physician who is independent and blinded (ward physician) is responsible for the actual discharge date.

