8.3 Study procedures

Randomization:

Computer-generated randomization (supported by our statistician) will be used with stratification for center. To ensure a balanced distribution, we will use block randomization.

Blinding and treatment allocation:

Blinding of the surgeons to the level of pressure and NMB is ensured by facing monitoring equipment away or covering these under sterile drapes. The level IAP will be set and adjusted by the anesthesiologist who is not blinded to the allocation of treatment. Surgical conditions will be assessed after introduction of the trocars, every 15 minutes or when the surgeon indicates inadequate surgical conditions. When SRS is ≤ 3 (table 1), pressure is increased with 2mmHg to max 14mmHg in group A and B or 16mmHg in group C and D. The anesthesiologist (not blinded) or his/her assistant titrates the dose of rocuronium to the desired level of NMB. The nerve stimulator and computer are placed behind the sterile drapes away from the surgeons. The research physician alongside the anesthetic staff will not be blinded in order to ensure depth of the NMB is continuously adequately monitored. To minimize the risk of observer bias and/or unblinding of the entire team, the following measures will be taken: Surgical adverse events will be registered directly after surgery by the blinded, primary surgeon. Surgeons, scrub nurses, postoperative care nurses, and ward physicians are blinded. Postoperative clinical outcomes (e.g. QoR-40 questionnaires) are collected by a blinded researcher.

Perioperative procedures:

The peri-operative flowchart is shown in figure 6.

During insufflations of the abdomen, the insufflator will be set at an intra-abdominal pressure of 8 or 14 mmHg. The usual dose of indocyanine green (0.2mg/kg) as regularly used will be injected intravenously. The camera trocar is aimed at the lateral abdominal wall and video is recorded for 3 minutes.

An overview of measurements and questionnaires for the primary and secondary endpoints, are given in table 3. Assessment of pain, PONV, discharge criteria and postoperative complications are part of normal medical treatment. Extra for this study, patients are asked to complete the QoR-40, SF-36 and McGill questionnaire. For the secondary endpoints on immune function, blood samples (a standard 6ml lithium/heparine, 10 ml EDTA tube and 2.5ml

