	Definitions	Modes of therapy
I	Any deviation from the normal postoperative course	No pharmacological or surgical treatment, endoscopic or radiological interventions were required. Acceptable therapeutic regimens are drugs such as anti-emetics, antipyretics, analgesics, diuretics and electrolytes and physiotherapy. Wound infections of small abscess requiring incision at bedside is within this category.
II	Normal course altered	Pharmacological management other than in grad 1. Blood transfusions and total parenteral nutrition are also included.
III	Complications that require intervention of various degrees	Sub-classified into: 
 - Grade IIIa – Complications that require an intervention performed under local anesthesia - Grade IIIb – Interventions that require general or epidural anesthesia
IV	Complications threatening life of patients (incl. CNS complication), requiring ICU support	Sub-classified into: 
 - Grade IVa - Single organ dysfunction (incl. dialysis) - Grade IVb – Multi-organ dysfunction
V	Death of a patient	

Table 3: Overview of study endpoints

	QOR-40 (primary endpoint in main study)	Anti-coagulated blood (ex vivo leukocyte responses, DAMP and cytokines)	Indocyanine green fluorescence of parietal peritoneum	Peritoneal tissue biopsy (histology and HIF1alpha mRNA)	Pain scores, PONV, Analgesia use	Complications, Discharge criteria, Length of hospital days	SF-36 QoL	McGill Pain Questionair
-1 day	X	X					X	
After trocar introduction			X	X				
At end of IAP				X				
1hr					X			
8 hr					X			
24 hr	X	X			X	X		
48 hr					X	X		
10-12 days	X	X					X	
3 months						X	X	X

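### Section 9.2.2 leaves non-serious wound infection and wound dehiscence unrecorded, in conflict with section 9.2.1 and with the Clavien-Dindo complication endpoint

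*Combined protocol and SAP*

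**What the plan says.** Four parts of the protocol bear on whether a minor wound infection enters the study data.

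- **Section 9.2.1** sets the general rule: "All adverse events reported spontaneously by the subject or observed by the investigator or his staff will be recorded".
- **Section 9.2.2** names events "considered to be inevitable in surgery and will not be recorded: blood loss <500 ml, surgical site infection and wound dehiscence". It then adds: "However, if any of these complications is considered an serious adverse event, they will be recorded". The exclusion therefore covers non-serious cases.
- **The summary and section 8.2** list the outcome "Postoperative complications scored by Clavien Dindo classification". The summary places it among the secondary endpoints. Table 2 gives the grading and says of grade I: "Wound infections of small abscess requiring incision at bedside is within this category". Table 3 marks complications at 24 hr, 48 hr and 3 months.
- **The rationale in the summary** argues for "better preservation of innate immune function which may help to reduce the risk of infectious complications". The aims at the end of section 1 include "clinical outcomes i.e. pain scores, quality of recovery and (infectious) complications".

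**The concern.** Site staff cannot follow 9.2.1 and 9.2.2 literally at the same time. A superficial wound infection seen on the ward must be recorded under one and left out under the other. The same infection counts as a complication under Table 2.

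What is at stake is the completeness of a secondary endpoint. If the exclusion is carried over to the complication data, grade I events (and any non-serious event of higher grade) of these two types drop out of both arms. If some staff apply it and others do not, ascertainment is inconsistent as well. A finding of no difference in complications would then be hard to interpret. The gap also falls on a type of event, infection, that the trial's own argument links to the intervention.

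**Working it through.** The plan states no figure on this point, so the check is mainly a comparison of texts.

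**1. Is the rule about recording or only about reporting?** The paragraph in 9.2.2 first deals with reporting of serious events to the ethics committee. The sentence on the three events, however, speaks of recording, and so does the exception for serious cases. As worded, it governs what is written down.

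**2. Does it conflict with 9.2.1?** Section 9.2.1 covers all adverse events and has no exception clause. Section 9.2.2 removes some of them. Neither refers to the other.

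**3. Does it overlap the endpoint?** Table 2 counts a wound infection opened at the bedside as grade I. Such an infection can be non-serious under the criteria in 9.2.2. The two sets therefore intersect.

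**4. Is there a separate stated route for complication data?**
- Section 8.3 says: "Assessment of pain, PONV, discharge criteria and postoperative complications are part of normal medical treatment". It names no form or source.
- The one registration step described for surgical adverse events is by the primary surgeon directly after the operation, too early for a wound infection that appears later.
- Table 3 gives a schedule but no data source.
- The table of secondary parameters in section 10.2 has no row for complications.

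Nothing says that Clavien-Dindo grades come from the adverse-event record. Nothing says that the endpoint is exempt from the exclusion.

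**5. Are the primary endpoints or the sample size touched?** No. With n per arm = 2(z₁₋α/₂ + z₁₋β)²σ²/δ² and the inputs of section 4.4 (90% power):
- QoR-40: 2(1.960 + 1.282)² × 15²/10² = 47.3, so 48.
- IL-6: 2(2.241 + 1.282)² × 4000²/3000² = 44.1, so 45.
- IL-10: 2(2.241 + 1.282)² × 65²/50² = 41.9, so 42.

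All three match the plan, and none uses complications.

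**6. How large could the loss be?** The documents give neither a rate of wound infection or dehiscence nor a non-serious share. The table is an illustration under **assumed** values only. Expected events are 48 × (p₁ + p₂). Power is the two-sided 5% normal approximation for two proportions. The last two columns assume that half of the events in each arm go unrecorded.

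| Assumed rates, control vs experimental | Events, all recorded | Power | Events, half unrecorded | Power |
|---|---|---|---|---|
| 5% vs 2.5% | 48 × 0.075 = 3.6 | 9% | 1.8 | 7% |
| 10% vs 5% | 48 × 0.15 = 7.2 | 15% | 3.6 | 9% |
| 20% vs 10% | 48 × 0.30 = 14.4 | 28% | 7.2 | 15% |

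The approximation is rough at such counts. An equal proportional loss in both arms leaves the risk ratio unchanged and halves the risk difference. Power is low in every row even with full recording, so loss of power is not the argument. The argument is incomplete ascertainment of a listed endpoint.

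**The case against.** The strongest reply is that the exclusion belongs to the safety chapter and the endpoint does not. Complications are listed in the summary and in 8.2, have their own column in Table 3, and are assessed in routine care. Section 3 has all endpoints arbitrated by a blinded researcher. Leaving expected surgical events out of the adverse-event log while still grading them as an outcome is a coherent design. On that view 9.2.2 is simply a specific exception to the general rule in 9.2.1.

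Much of this stands. A reader might infer that the endpoint is bound to lose these events, and the documents do not establish that: the separate schedule in Table 3 leaves the separate-log reading open. But the reading has to be supplied by the reader, because the only explicit instruction about recording a minor wound infection is not to do so. Arbitration can work only on what has been written down. Treating 9.2.2 as an exception to 9.2.1 removes the first conflict but confirms the exclusion, so the overlap with Table 2 remains.

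Other stronger readings also go too far:
- Infectious complications are named in the aims but are not a listed endpoint with an analysis of their own.
- The immune argument concerns infection. Nothing predicts a difference in wound dehiscence.
- Wound infection is not singled out as the main clinical expression of the mechanism. Section 1 also links immune status to pain and fatigue.

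**Conclusion.** The point holds as an unreconciled exclusion. Section 9.2.2 conflicts with 9.2.1 as written and overlaps grade I of a listed secondary endpoint, and no text says that the endpoint is exempt. Non-serious wound infections and dehiscences can therefore be missing from the Clavien-Dindo comparison. Whether they will be depends on how the complication data are collected, which the documents do not say.

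The size of any loss cannot be calculated from the documents, and the assumed rates above show only that the comparison is weak in any case. Serious cases and other infections are still recorded. The primary endpoints and the 48 per arm do not depend on this. It should be corrected because the ambiguity is avoidable and bears on events the rationale cares about, but it does not threaten the trial's main conclusions.

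**What to change.** Either of two changes is enough:

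- delete surgical site infection and wound dehiscence from the list of unrecorded events in 9.2.2; or
- keep the list, but state there that these two events are exempt from adverse-event reporting only, and that they are always recorded and graded for the Clavien-Dindo endpoint at the Table 3 complication time points (24 hr, 48 hr and 3 months).

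With the second option, 9.2.1 should refer to the exemption so that the two sections agree. If a separate complication form already exists, the added sentence only confirms it.

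The cost is one sentence (plus the cross-reference under the second option) and one case-report-form item. Complications are already assessed in routine care, so no visits or patients are added.

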9.2.3 Suspected Unexpected serious adverse reactions (SUSAR's)

Not applicable

9.3 Annual safety report

Not applicable

9.4 Follow-up of adverse events

All AEs will be followed until they have abated, or until a stable situation has been reached. Depending on the event, follow up may require additional tests or medical procedures as indicated, and/or referral to the general physician or a medical specialist.

SAEs need to be reported till end of study within the Netherlands, as defined in the protocol.

9.5 Data Safety Monitoring Board (DSMB)

The need for a DSMB is assessed taking the EMEA guidelines on data monitoring committees into consideration. We believe that an interim evaluation does not increase patient safety, because safety of the procedure has already been proven. Study conduct and progress will be monitored according a monitor plan. Thus, a DSMB is not beneficial considering the proposed study design and will therefore not be established.

10 STATISTICAL ANALYSIS

The principal investigator (PI) has final responsibility regarding the data; a web-based encrypted data management system will be used to minimize errors, to ensure traceability and privacy of the subjects. An independent statistician will provide assistance for data-analysis. The data will be unblended after completion of the follow-up period and identification of protocol violations.

10.1 Primary study parameter(s)

- Quality of recovery score (QoR-40) at postoperative day 1.
- For QOR-40 score, factorial ANCOVA will be used to compare groups and to adjust for co-variates *i.e.* age and gender. P-values <0.05 will be considered statistically significant.
- IL-6 response upon whole blood LPS stimulation at postoperative day 7.
- For mononuclear cell responsiveness, ANCOVA will be used to compare groups and to adjust for co-variates *i.e.* age and gender. As the primary endpoint includes changes in both IL-6 and IL-10 release, Bonferroni correction for multiple comparisons will be used. P-values < 0.025 will be considered statistically significant.
- Perfusion index in sigmoid as calculated from the slope of ICG fluorescence intensity, and time to maximal intensity in seconds. (extracted from video registration).
- Factorial ANCOVA will be used to compare groups and adjust for covariates *i.e.* age and gender. P-values <0.05 will be considered statistically significant.

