4.2 Inclusion criteria

To participate in this trial, a subject must meet all of the following criteria:

- Age \geq 18 years
- Undergoing elective robot assisted radical prostatectomy (RARP)
- Obtained informed consent

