4.4 Sample size calculation

The main study includes 48 patients per study arm (low impact and standard laparoscopy). With this number of patients we will have sufficient power for the primary and secondary analyses:

- 1) Quality of recovery at POD 1 as reflected by the QoR-40 questionnaire. Although Myles et al. reported a minimal clinically relevant difference (MCID) of 6.3 for the QoR-40 questionnaire, consensus about the MCID is lacking. As 6.3 is a relatively small difference on a scale ranging from 40-200, we feel that a MCID of 10 points is more appropriate. A sample size of 48 patients per group is needed to provide 90% power to detect a 10 point difference in the QoR-40 at POD 1 (alpha 5%) with an estimated standard deviation of 15.
- 2) Innate immune function as reflected by the *ex vivo* release of IL-6 and IL-10 upon LPS stimulated leukocytes at POD 7. A sample size of 45 patients per group is needed to provide 90% power to detect a 3.000 pg/mL difference in IL-6 release (alpha 2.5%) with an estimated standard deviation of 4.000 pg/mL at POD 7. A sample size of 42 patients per group is needed to provide 90% power to detect a 50 pg/mL difference in IL-10 release (alpha 2.5%) with an estimated standard deviation of 65 pg/mL. As two cytokines are measured, a Bonferroni correction was used (alpha 2.5%).

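### The primary ANCOVAs adjust for gender, which cannot vary in a prostatectomy trial, and omit the baseline QoR-40 and cytokine values the trial already collects

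*Combined protocol and SAP*

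**What the plan says.** Section 10.1 sets out three primary analyses, each an ANCOVA with age and gender as covariates. For recovery: "For QOR-40 score, factorial ANCOVA will be used to compare groups and to adjust for co-variates *i.e.* age and gender". For the LPS-stimulated cytokines: "For mononuclear cell responsiveness, ANCOVA will be used to compare groups and to adjust for co-variates *i.e.* age and gender". The perfusion index gets the same two covariates, again in a factorial ANCOVA.

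The inclusion criteria (section 4.2) admit only patients having a radical prostatectomy.

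Section 8.2 schedules baseline measurements of both outcomes. It lists "Quality of recovery score (QoR-40) at 1 day before surgery and day 10-12 after surgery", and for the immune measures "Plasma levels of DAMPs, cytokines and ex vivo immune function at baseline, 24 hours after surgery and 10-12 days after surgery". Table 3 marks both in its row for the day before surgery. Neither value appears in any model in section 10.

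For the cytokines, section 10.1 justifies the Bonferroni correction with the words "As the primary endpoint includes changes in both IL-6 and IL-10 release". The endpoint it lists, however, is a response at one postoperative time, and no change from baseline is defined.

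**The concern.** There are two faults in the covariate list.

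- **Gender does nothing.** It is the same for every participant, so the term is not estimable. The model that would be fitted adjusts for age alone, which is not the model described.
- **Baseline is left out.** A pre-surgery value of the same questionnaire or assay is generally a natural candidate for explaining variation in the later value. Omitting it leaves that variation in the residual, so the confidence interval is wider than it need be. A chance imbalance at baseline between two arms of 48 also goes uncorrected in the estimate.

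Two wording problems add to this. The reference to changes in cytokine release leaves unclear whether postoperative values or change scores will be analysed. And *factorial* does not fit a design with one two-level factor.

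What is at stake is precision and clear prespecification of the primary tests, not bias.

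**Working it through.** **1. The plan's own sample sizes.** Inputs are from section 4.4. For QoR-40 the trial is sized to "detect a 10 point difference in the QoR-40 at POD 1 (alpha 5%) with an estimated standard deviation of 15", and "A sample size of 48 patients per group is needed to provide 90% power". For IL-6 the difference is 3,000 and the SD 4,000 pg/mL; for IL-10 they are 50 and 65 pg/mL; both use alpha 2.5%. Sidedness is not stated; two-sided reproduces the plan.

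n per arm = 2 (z₁₋α/₂ + z₀.₉₀)² SD² / d²

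- QoR-40: 2 × (1.960 + 1.282)² × 15²/10² = 47.3, so 48.
- IL-6: 2 × (2.241 + 1.282)² × 4000²/3000² = 44.1, so 45.
- IL-10: 2 × (2.241 + 1.282)² × 65²/50² = 41.95, so 42.

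All three match. One-sided tests would give 39, 38 and 36. The sample size therefore takes no credit for any covariate.

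**2. The gender term.** With 96 patients and columns for intercept, arm, age and gender, a constant gender column duplicates the intercept. The design matrix has rank 3, not 4, so no gender coefficient exists.

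**3. What baseline would add.** If ρ is the correlation between the baseline and postoperative values, adjustment reduces the residual SD to SD × √(1 − ρ²). Equivalent n per arm is 48/(1 − ρ²). Power is from the noncentral t with 2 × 48 − 3 = 93 degrees of freedom and noncentrality d / (residual SD × √(2/48)). Half-width is 1.986 × residual SD × √(2/48).

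For QoR-40:
- ρ = 0: 15 × √(2/48) = 3.06; noncentrality 10/3.06 = 3.27; half-width 1.986 × 3.06 = 6.1.
- ρ = 0.5: residual SD 15 × √0.75 = 12.99; 12.99 × √(2/48) = 2.65; noncentrality 3.77; half-width 5.3.

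The documents give no ρ, so every row below ρ = 0 is an assumption.

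| Assumed ρ | QoR-40 residual SD | QoR-40 power | QoR-40 95% CI half-width | Equivalent n per arm | IL-6 power (alpha 2.5%) | IL-10 power (alpha 2.5%) |
|---|---|---|---|---|---|---|
| 0 | 15.0 | 89.8% | 6.1 | 48 | 91.7% | 93.0% |
| 0.2 | 14.7 | 91.0% | 6.0 | 50 | 92.8% | 94.0% |
| 0.3 | 14.3 | 92.3% | 5.8 | 53 | 94.0% | 95.1% |
| 0.5 | 13.0 | 96.2% | 5.3 | 64 | 97.4% | 98.0% |
| 0.6 | 12.0 | 98.1% | 4.9 | 75 | 98.9% | 99.2% |

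Age is in both the planned and the proposed model and is left out of these sums. Read ρ as the correlation remaining after age is accounted for.

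**4. Cost of the extra term if baseline is useless.** At ρ = 0, QoR-40 power is 89.84% without the added degree of freedom and 89.83% with it.

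**5. Chance imbalance.** If the baseline SD were also 15 (an assumption), the standard error of the arm difference at baseline would be 15 × √(2/48) = 3.1 points, against a target difference of 10.

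**The case against.** The strongest reply is that this concerns efficiency only. Randomisation makes the comparison unbiased without baseline, the nominal 90% power was obtained from unadjusted SDs, and chance imbalance is sampling variation that the confidence interval already covers. Statistical software will drop a constant covariate. All of this is correct, and it is why the point is not one of validity.

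The size of the gain is also unknown. A score taken before surgery may correlate only weakly with one taken the day after it. At ρ = 0.2 power rises by about one percentage point and the half-width falls by about 0.1 point. That stands too. But the downside is negligible (step 4), and the 90% depends on SD 15 holding. If the SD were 18 (an assumption), power by the normal approximation would be 77.7% unadjusted and 88.2% with ρ = 0.5.

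The covariate list may have been meant as examples. If so, the primary models are not prespecified, and the text needs correction on that reading as well. The mention of changes in cytokine release may mean differences between arms, or may imply that baseline is used; it cannot be settled from the text, which is a reason to state the model.

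Two further points are fair. A complete-case ANCOVA would lose patients without a baseline value, so a rule is needed. And the IL-6 and IL-10 figures use the SDs given for day 7, whereas sections 8.1 and 8.2 and Table 3 refer to days 10-12. That conflict is a separate matter, but SD and ρ both depend on how it is resolved.

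**Conclusion.** The concern holds. As written, one of the two covariates in every primary model is empty, and the baseline values of QoR-40 and of the ex vivo cytokine responses are collected but unused. The planned tests remain valid and the stated sample sizes are correct for an unadjusted comparison.

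The loss is in precision: close to nothing if the baseline-outcome correlation is 0.2 or less, moderate at 0.3, and a quarter of the variance at 0.5. These figures rest on assumed correlations and on the SDs in section 4.4. The omission itself rests on no assumption. Because the data are already in hand, the change should be made.

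**What to change.** In section 10.1:

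- For QoR-40 and for each of IL-6 and IL-10, replace age and gender by age and the day -1 value of the same outcome.
- For the perfusion index, which is recorded once, after trocar introduction, and has no earlier measurement, adjust for age only.
- Describe the model as an ANCOVA with treatment arm as the factor, in place of factorial ANCOVA.
- State that the cytokine outcome is the postoperative value adjusted for baseline, so that the reference to changes is no longer ambiguous.
- Say how a missing baseline is handled, so that those patients stay in the analysis; for example, impute the baseline mean pooled over both arms.

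The cost is one degree of freedom per model and a change of wording. No new data are needed. The amendment should be dated before the unblinding described in section 10, so that it counts as prespecified.
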